13.2 Analysis plan

A detailed statistical analysis plan (SAP) will be developed and finalised prior to the locking of the trial database in consultation with the trial steering committee.

We will conduct an intention-to-treat analysis (all randomised participants) and per-protocol analysis (completing participants with 75% compliance).

Primary endpoint:

Urine NTX at six months in postmenopausal osteopenic or osteoporotic women with baseline serum selenium below 120 mcg/l

Baseline data will be assessed for comparability between the treatment groups. NTX/Cr will be assessed visually for normality and if it is non-Normal a log-transform will be applied, with results reported as percentage difference between geometric means. Analysis of covariance (ANCOVA) will be used to compare mean NTX/Cr between the groups adjusting for baseline NTX/Cr measurements. The Hochberg procedure will be used to account for multiple comparisons; P-values are ordered from smallest to largest. If the largest P-Value is less than 0.05 then all null hypotheses can be

rejected. If not, if the second P-value is less than 0.05/2, then all bar the largest can be rejected, and so on (SA Julius, An Introduction to Statistics in Early Phase Trials).

Secondary endpoints:

Urine NTX at three months: analysis as described for the primary endpoint

Serum selenium, SePP, serum CTX, PINP, osteocalcin, thyroid function, glucose and insulin at three and six months: analysis as described for the primary endpoint.

BMD by DXA at six months: analysis as described for the primary endpoint.

We will examine impact of baseline selenium levels on the NTX response to selenium supplementation by fitting a linear model with NTX at follow-up as the dependent variable and baseline selenium, baseline NTX and dose as independent variables. With n=66 (receiving active treatment) the minimum correlation that can be detected with 90% power and 5% significance level is 0.44.

Short physical performance battery, grip strength, hydroperoxidases, glutathione peroxidase activity, highly sensitive CRP, IL-6 analysis as described for the primary endpoint.

There is no planned interim analysis of outcome measures. There will be an interim analysis of baseline serum selenium to determine the final sample size.

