8. PLANNED INTERVENTIONS

The intervention is a medicinal product containing sodium selenite. We will study two doses: 50 and 200mcg daily. The preparation is sodium selenite tablets 'Selenase' 50mcg and 200mcg (Biosyn, Germany). The tablets will be overencapsulated and a matching placebo will be manufactured to maintain the blind.

The mean difference between selenium levels in a replete population (USA) and the UK is about 60mcg/L. The mean increase in serum selenium with 200mcg/day is 90 mcg/L (19). 200mcg/day is a clinically effective dose in Graves' ophthalmopathy. Therefore 200mcg will be enough to achieve repletion in the majority of subjects and to determine whether selenium repletion has a clinically significant effect on bone turnover. If we see no effect at this dose we will be confident to accept the null hypothesis.

The 50mcg dose will assess whether a lower dose might be effective for musculoskeletal health – if its effect on bone turnover is similar to the 200mcg dose we could recommend the 50mcg dose for clinical use, at lower cost and lower risk of adverse effects.

This is a short, low risk study of a medication that we expect to be well tolerated. We are very experienced in recruiting and retaining patients in clinical trials. We expect compliance to be good and loss to follow-up to be low (less than 10%). We will make telephone contact with participants between study visits (every month) to maintain their engagement and check for adverse effects.

The required minimum sample size for the primary endpoint is 21 per group. We will recruit 33 per group into the primary analysis to allow for drop-out, group imbalance and secondary endpoint analysis.

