11.7 Dosage modifications

There are no planned dose modifications.

If a participant develop diabetes (fasting glucose $\geq 7.0\text{mmol/l}$) or thyroid dysfunction (TSH outside the reference range and determined as clinically significant by the investigator) during the study (identified on safety monitoring bloods, or a new diagnosis reported by participant at monthly contact), their treatment will be stopped. If a participant experiences other adverse effects thought to be related to IMP the PI will decide if that participant should stop treatment.

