13. STATISTICS

13.1 Power calculation

A 20% (10nmol BCE/mmolCr) decrease in urine NTX is a plausible and clinically significant effect size.

In a previous study, 200mcg daily for six months increased serum selenium by 90mcg/L (19).

In our observational study of serum selenium and bone turnover markers, the regression coefficient of serum selenium and NTX/Cr was -0.101 (9), so if the relationship were causative we would expect an increase in serum selenium of 90mcg/L to be associated with a reduction in urine NTX/Cr of 9 nmol BCE/mmolCr (approximately 20%).

In support of this estimate, we would not expect as large a change in bone turnover as would be seen with a potent anti-resorptive drug such as a bisphosphonate (about 60%), but it might be

similar to a weaker anti-resorptive such as a SERM. In a study of six months' treatment with the SERM lasofoxifene (37), NTX decreased by 29%. We have also used this study as a model for the likely SD (12.5) and the correlation between NTX/Cr at baseline and six months (0.7).

A 20% decrease in NTX is clinically significant; a 20% decrease in NTX (about 1 standard deviation decrease) with bisphosphonate treatment is associated with a 30% decrease in incident vertebral fracture (38).

To achieve 90% power to detect this mean difference at the 2.5% (two-sided) level will require 21 patients per group. To allow for dropout, group imbalance and the secondary endpoint analyses we will recruit 33 patients per group with serum selenium below 120mcg/l (99 patients in total).

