APPENDIX 2 – Schedule of procedures

	Screening	Baseline	4W	8W	13W	17W	21W	26W	30W
Informed consent	X								
Medical history for eligibility	X								
DXA BMD*	X	X						X	
Colecalciferol 100,000 units	X								
Practice placebo (optional)	X								
Screening bloods ¹	X								
Blood for DNA		X							
Serum selenium		X			X			X	
Height and weight		X			X			X	
Pulse and blood pressure		X			X			X	
Bloods for end-of-study analysis ²		X			X			X	
Urine for end-of-study analysis ³		X			X			X	
Physical function tests		X			X			X	
Diet diary		X						X	
Concomitant medications		X	X	X	X	X	X	X	
Randomisation		X							
Dispensing of study drug		X			X				
Safety bloods ⁴					X			X	
Compliance check			X	X	X	X	X	X	
Adverse events		X	X	X	X	X	X	X	X

*DXA will be done at screening for patients without BMD measurement in the last 6 months, and not repeated at baseline. For patients with BMD measurement within the last 6 months this measurement will be used for eligibility, and BMD will be measured at baseline.

1. Glucose, , HbA1c, TSH, bone profile, creatinine (non-fasted)
2. Selenium, selenoprotein P, PINP, OC, CTX, glutathione peroxidase, reactive oxygen species, hsCRP, IL-6, 25OH vitamin D
3. NTX/Cr
4. At baseline: glucose and insulin. At 13w and 26w: glucose, insulin, HbA1c, TSH

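### The primary analysis named in section 13.2, a six-month ANCOVA on baseline NTX/Cr, makes no use of week-13 NTX from women who have no week-26 urine; using it brings a modest gain for a change of wording

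*Protocol*

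**What the plan says.** **Model.** Protocol 13.2 sets the primary endpoint as urine NTX at six months in women with baseline serum selenium below 120 mcg/l. The method is: "Analysis of covariance (ANCOVA) will be used to compare mean NTX/Cr between the groups adjusting for baseline NTX/Cr measurements". No other covariate or visit enters. Three-month NTX is a secondary endpoint with its own ANCOVA of the same form.

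**Analysis set.** 13.2 also states: "We will conduct an intention-to-treat analysis (all randomised participants"). Section 6 ties intention-to-treat to the primary endpoint by requiring at least 99 randomised women below 120 mcg/l for it. For the primary test the promise therefore covers every randomised woman in that stratum.

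**Data collected.** In Appendix 2 the row "Urine for end-of-study analysis" (NTX/Cr) is marked at baseline, 13W and 26W. Safety bloods are taken at 13W and 26W.

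**How women can be lost.**
- 11.7: for diabetes or clinically significant thyroid dysfunction found on safety bloods or newly diagnosed, "their treatment will be stopped".
- Sections 12 and 20 speak of withdrawing women for the same two conditions. Section 20 adds other reasons, such as needing a prohibited medication.
- 11.10 withdraws women who miss, or refuse blood at, the three-month safety check.
- Section 20 asks women who stop study drug to continue assessments where they are willing and it is possible.

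**Missing values.** The protocol does not say how a missing 26W NTX is treated. 13.2 leaves detail to a SAP, which is not among the documents available here.

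**The concern.** A single-visit ANCOVA needs the 26W value. Applied to observed data, it analyses women with both baseline and 26W NTX, which is narrower than the set 13.2 describes. A woman who leaves after the 13W visit would normally have given baseline and 13W urine. Her 13W NTX will be assayed anyway for the secondary endpoint, yet it does not inform the primary contrast.

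The timing is relevant. The 13W visit yields both the NTX sample and the glucose and TSH results that can end treatment or participation. Section 3 lists thyroid dysfunction and diabetes as possible adverse effects of selenium. If such losses occurred, differed by arm and were related to bone turnover, an observed-case comparison could be biased. Part of the information needed to reduce that bias would already have been collected. A small loss of precision is also at stake.

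**Working it through.** **1. Reproduce the plan's sample size.** Inputs from 13.1: SD 12.5; baseline to six-month correlation 0.7; "A 20% (10nmol BCE/mmolCr) decrease in urine NTX is a plausible and clinically significant effect size"; and "To achieve 90% power to detect this mean difference at the 2.5% (two-sided) level will require 21 patients per group". 13.1 also derives a reduction of 9, so both values are carried below.

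- ANCOVA residual SD = 12.5 × √(1 − 0.7²) = 8.927.
- Difference 10: n = 2 × 8.927² × (2.241 + 1.282)² / 10² = 19.8, so 20 per group. Adding 2.241²/4 gives 21.04, and the noncentral t gives 22.
- Difference 9: 25 by the normal approximation.

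The stated 21 is reproduced with the ANCOVA variance and a difference of 10. The sample size therefore rests on the same baseline-adjusted six-month comparison.

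**2. Observed-case ANCOVA at 10% loss.** Section 8 expects loss below 10%. With 33 recruited per arm, 33 × 0.9 = 29.7 remain. The standard error of a contrast is 8.927 × √(2/29.7) = 2.32. Power at two-sided 2.5% is 98.10% (difference 10) or 94.99% (difference 9). Loss could reach 1 − 21/33 = 36% before the arm fell below 21.

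**3. Gain from the 13W values.** The protocol gives no 13W correlations. Assumed: baseline to 13W 0.7; 13W to 26W ρ = 0.7 to 0.9; and either half or all of the lost women having a 13W sample.

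- Partial correlation of 13W and 26W given baseline = (ρ − 0.49)/(1 − 0.49).
- Effective n = n_obs / (1 − f × partial²), where f is the share of women with any follow-up NTX who have 13W only.
- If all lost women have a 13W sample, f = 0.10.

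| ρ | Partial | Effective n (half / all) | Power %, difference 10 | Power %, difference 9 |
|---|---|---|---|---|
| 0.7 | 0.41 | 30.0 / 30.2 | 98.19 / 98.27 | 95.17 / 95.32 |
| 0.8 | 0.61 | 30.3 / 30.8 | 98.29 / 98.45 | 95.37 / 95.71 |
| 0.9 | 0.80 | 30.7 / 31.8 | 98.43 / 98.69 | 95.65 / 96.21 |

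With all lost women sampled at 13W, the information gain is 1/(1 − 0.1 × 0.41²) = 1.02 up to 1/(1 − 0.1 × 0.80²) = 1.07, that is 2% to 7%. Across the table, power rises by 0.1 to 1.2 points. At 20% loss, effective n goes from 26.4 to between 26.9 and 30.3, and power at a difference of 9 goes from 92.2% to between 92.7% and 95.4%.

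**4. Bias, by assumption only.**

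- *Loss in one arm.* Suppose 10% are lost from the 200 mcg arm and none from placebo, and the lost women are 5 to 10 nmol higher given baseline. The observed-case bias is 0.10 × 5 = 0.5 to 0.10 × 10 = 1.0 nmol in favour of 200 mcg. If the whole shift is already present at 13W, a model using 13W leaves (1 − partial) of it. For the 1.0 case that is 0.59, 0.39 or 0.20. If the shift appears only after 13W, the model removes none of it.
- *Loss depending on 13W NTX.* Simulation with a true effect of −10 and 5% to 10% missing per arm. Observed-case ANCOVA gave about −9.9 when the mechanism was the same in both arms, and −9.6 to −9.8 when it acted in placebo only. Using 13W NTX gave about −10.0. The largest bias was about 4% of the effect, here towards no effect.

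**The case against.** The case for leaving 13.2 alone is strong.

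- **Silence is not a rule.** A reader might infer that the protocol drops women without a 26W urine. It does not say so. Missing-data handling is commonly left to the SAP that 13.2 announces.
- **The model and the set are compatible.** A reader might infer that the ANCOVA cannot deliver an intention-to-treat analysis. It can: after multiple imputation that includes 13W NTX, the same ANCOVA keeps every woman.
- **The 13W data are not thrown away.** They are analysed as a secondary endpoint. They are unused only in the six-month contrast.
- **Stopping treatment is not loss of the 26W urine.** Section 20 asks women who stop to continue assessments, although only where willing and possible.
- **A repeated-measures model does not complete the set either.** Women who miss the three-month visit and are withdrawn under 11.10 would usually have neither 13W nor 26W NTX.
- **The bias sizes restate their inputs.** No protocol figure supports 10% loss in one arm and none in the other, or a shift as large as the target effect. Section 7.2 excludes diabetes and thyroid dysfunction at entry. Sections 3 and 12 cite earlier use at this dose without such harms.
- **ANCOVA at the primary time point is standard** and matches the power calculation.

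All of this stands, and it limits the point. It does not remove it, because 13.2 itself chooses the visit, the model and the covariate, and places 13W NTX in a separate analysis. On its plain reading the primary contrast makes no use of 13W NTX, and a better choice is available at little cost.

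**Conclusion.** The point holds in a limited form. As written and run on observed data, the primary analysis covers fewer women than the stated intention-to-treat set and ignores 13W NTX from women lost later. The protocol's withdrawal rules make such losses possible.

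The size is modest: the step 3 gains are small because 33 per arm already leaves ample power, and they rest on assumed 13W correlations. The better argument is the weaker missing-data assumption: missing at random given baseline and 13W NTX, rather than given baseline alone. The protection is partial and depends on the relevant NTX difference being visible by 13W.

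A reader might go further and infer that the six-month contrast will be biased towards 200 mcg. The documents do not support that. Differential loss and the NTX shift are both assumed, the direction depends on the mechanism, and even the largest assumed bias of 1.0 nmol is less than half the standard error of about 2.3.

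**What to change.** In 13.2, for women with baseline selenium below 120 mcg/l, name one of two primary analyses:

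- a repeated-measures model of 13W and 26W NTX/Cr with baseline NTX/Cr by visit, arm by visit and unstructured covariance, including every such woman with at least one post-baseline NTX; or
- the existing 26W ANCOVA after multiple imputation that includes 13W NTX.

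Keep the 26W contrasts under Hochberg as the primary tests, on the scale chosen by the existing log-transform rule. Keep the observed-case 26W ANCOVA as a sensitivity analysis. Under the first option the secondary 13W contrast can come from the same model. State how many women have neither 13W nor 26W NTX, since the repeated-measures model does not include them.

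The cost is protocol and SAP wording, settled before unblinding. No visit, sample or assay is added, because 13W NTX is already to be measured. With complete data the repeated-measures result is essentially that of the ANCOVA. The downside is a slightly more complex model and reliance on data being missing at random given baseline and 13W NTX.

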5. HYPOTHESIS AND OBJECTIVES

Hypothesis: Selenium supplementation decreases bone turnover in postmenopausal women with low bone density by reducing pro-resorptive reactive oxygen species.

Purpose: to determine if selenium supplementation is beneficial for osteoporosis prevention and muscle function in postmenopausal women.

Objectives: to determine if six months selenium supplementation in postmenopausal women with osteopenia or osteoporosis

- decreases bone turnover
- increases bone density
- improves physical function score and grip strength
- is safe (particularly for thyroid function and diabetes)
- is well-tolerated
- decreases markers of oxidative stress and inflammation

All of these objectives will be answered at the completion of the study and analysis, with a total project duration of 26 months.

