We will measure serum selenium concentration at screening, baseline, three months and six months to evaluate the magnitude of effect of the study doses on serum selenium levels. The available data suggest that the optimum serum selenium concentration is 130 to 150 mcg/l, and nearly everyone in the UK has serum selenium concentrations below this range (8). The population range of serum selenium in the USA is 80 to 200 mcg/l. We expect that a dose of 200mcg/day will increase serum selenium by an average of 90mcg/l so the number of women whose serum selenium might increase above 200mcg/l is small.

Selenium has a role in thyroid function. There is a reported association of high blood selenium with type 2 diabetes, although this was not confirmed in a prospective study with doses of 100 to 300 mcg/day for 6 months (19). We will exclude volunteers with diabetes or thyroid dysfunction at screening, and measure thyroid function, fasting glucose and insulin at screening/baseline, three months and six months. We will withdraw participants who develop thyroid dysfunction or diabetes during the study. We will analyse between-group differences in change in thyroid function tests and blood glucose as a secondary endpoint.

The data on serum selenium concentration, glucose, thyroid function and any possible symptoms of toxicity will be reviewed by the DMEC.

The study procedures (DXA bone densitometry, blood and urine sampling and muscle function tests) carry negligible risks to the participants.

The radiation dose has been assessed by a Radiation Protection Supervisor and Clinical Radiation Expert.

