17. RANDOMISATION

Participants will be block randomised equally to the three treatment arms.

The randomisation list will be generated by Sharp Clinical Services. The list will be supplied to STH pharmacy and a copy retained by Sharp.

At randomisation, participants will be allocated a study ID number which corresponds to their randomised medication number (the ID number will be in the format SE???, where ??? is the randomised medication pack number).

The code list will be stored in STH pharmacy, in a sealed signed envelope under the supervision of the study pharmacist, or out-of-hours duty pharmacist. This envelope is signed when opened and resealed for audit purposes. If emergency access is required out of hours, the PI or if unavailable, another metabolic bone consultant can be contacted through STH switchboard. If they agree that the code need to be broken, the duty pharmacist will access the list.

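### Section 13.2 carries the Hochberg step over to the thyroid, glucose and insulin group comparisons, so a difference at one dose only is harder to declare in the formal safety analysis

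*Protocol*

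**What the plan says.** Section 13.2 of the protocol describes the primary analysis as ANCOVA on NTX/Cr with baseline adjustment, and adds: "The Hochberg procedure will be used to account for multiple comparisons". The steps are spelled out. First, "If the largest P-Value is less than 0.05 then all null hypotheses can be" rejected. Failing that, "if the second P-value is less than 0.05/2, then all bar the largest can be rejected".

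Among the secondary endpoints, one line groups serum selenium, SePP and the bone markers with the safety variables: "thyroid function, glucose and insulin at three and six months: analysis as described for the primary endpoint". No exception is made for safety.

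Section 5 lists as an objective to determine whether supplementation "is safe (particularly for thyroid function and diabetes"). Section 12 confirms the group-level comparison: "We will analyse between-group differences in change in thyroid function tests and blood glucose as a secondary endpoint". Section 17 fixes the design: "Participants will be block randomised equally to the three treatment arms".

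**The concern.** Hochberg limits false positive claims over the two doses. That suits efficacy, where the error to guard against is claiming a benefit that is not there. For thyroid function and glucose the costlier error runs the other way. With two dose-versus-placebo comparisons, Hochberg changes a conclusion in exactly one situation: one dose has p between 0.025 and 0.05 and the other has p of 0.05 or more. A harm concentrated at one dose can produce that pattern, and section 8 itself expects a lower risk of adverse effects at 50 mcg than at 200 mcg. An unremarkable result at one dose would then raise the bar for the other.

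At stake is the formal end-of-trial comparison that addresses the safety objective. The protocol's power calculation covers NTX only, so the safety comparisons have no planned power from which to absorb a loss.

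**Working it through.** **The plan's own use of the 2.5% level.** Section 13.1 states: "To achieve 90% power to detect this mean difference at the 2.5% (two-sided) level will require 21 patients per group". Inputs there are a difference of 10, SD 12.5 and baseline correlation 0.7. The ANCOVA SD is 12.5 × √(1 − 0.7²) = 8.93. The normal approximation gives n = 2 × 8.93² × (2.241 + 1.282)² / 10² = 19.8, so 20 per group; the noncentral t gives 22. The stated 21 is reproduced to within one patient. For NTX, therefore, the stricter Hochberg level is already paid for in the sample size. Nothing comparable is stated for thyroid function, glucose or insulin.

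**Cost of the stricter level.** The critical z moves from 1.960 (two-sided 0.05) to 2.241 (two-sided 0.025). The difference detectable with 80% power grows by (2.241 + 0.842) / (1.960 + 0.842) = 1.10, that is by 10%.

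**Power to declare a shift at one dose.** The two z statistics share the placebo arm, so with equal arms their correlation is 0.5. Hochberg rejects for the affected dose if its p is below 0.025, or if both p-values are below 0.05. Set the affected dose's mean z at 1.960 + 0.842 = 2.802, which gives 80% unadjusted power.

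- Probability of p < 0.025: 71.2%.
- Added by p between 0.025 and 0.05 with the other dose also below 0.05: 0.3 points if the other dose has no effect, 1.3 points at half the effect, 6.3 points at the same effect.

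| Other dose | Unadjusted | Hochberg |
|---|---|---|
| No effect | 80% | 71.5% |
| Half the effect | 80% | 72.5% |
| Same effect | 80% | 77.5% |

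With no effect at the other dose, 90% unadjusted power becomes 84.5%, and 50% becomes 39.2%. A separate simulation with t-tests at 33 per arm and a shift of 0.7 baseline-adjusted SD gives 80% and 72%.

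**What size of shift this is.** The documents give neither an effect size nor a baseline correlation for these variables, so this part is assumption. In raw SD units the shift with 80% unadjusted power is 2.80 × √[(2/n)(1 − r²)].

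| Per arm | r = 0.7 | r = 0.5 | r = 0 |
|---|---|---|---|
| 33 | 0.49 | 0.60 | 0.69 |
| 40 | 0.45 | 0.54 | 0.63 |
| 55 | 0.38 | 0.46 | 0.53 |

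The arm sizes are the low-selenium primary set (33), the expected total of 120 (40) and the maximum of 165 (55). Section 13.2 does not say whether the cross-reference brings the selenium restriction with it. The loss from 80% to about 72% depends on neither n nor r; only the SD attached to it does. Dropout is not applied.

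**Number of comparisons.** The text does not say whether two or three pairwise comparisons enter Hochberg. With three, at 33 per arm and 0.5 adjusted SD, power falls from 52% to 37.5%; with two it falls to 41%.

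**Price of removing the step.** With no effect at either dose, the chance of at least one rejection is 4.8% under Hochberg and 9.1% unadjusted, per variable and visit. Over three variables and two visits, treated as independent (an upper illustration, since the measures are correlated), these become 1 − 0.952⁶ = 26% and 1 − 0.909⁶ = 44%.

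**The case against.** A reader might infer that participants are less well protected during the trial. The documents do not support that. Section 10.2 has a doctor assess every out-of-range value, section 11.7 sets individual treatment stopping, and section 23 gives the DMEC unblinded glucose, insulin and thyroid data. None of these uses Hochberg.

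A reader might also infer that the protocol will call selenium safe because an adjusted test is not significant. No section says so. The wording in section 8 about accepting the null hypothesis concerns bone turnover.

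Further, Hochberg as written orders p-values and leaves estimates and intervals alone, so ordinary 95% intervals could be reported under the present text. The SAP, which is not at hand, may confine the cross-reference to the ANCOVA model. A wholly null second dose is the unfavourable case, and a dose-related harm could equally leave a smaller effect there. Sample size is the larger limit: at 33 per arm and 0.5 adjusted SD the unadjusted test still misses about 48%. Consistent error control over all secondary endpoints is a defensible convention.

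Most of this stands and confines the point to one formal label. It does not remove the point. The rule is stated in the protocol rather than left open, and half an effect at the second dose recovers only about one percentage point.

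**Conclusion.** The point holds in limited form. On the text, the group comparisons of thyroid function, glucose and insulin inherit Hochberg, which works against the purpose of a stated safety objective. For a shift at one dose with 80% unadjusted power, the formal comparison loses about 8 points; the loss is 2 to 3 points if both doses carry the same effect. These figures assume two comparisons, equal arms and a shared placebo. The corresponding shift, about 0.38 to 0.69 SD, rests on assumed arm sizes (33 to 55) and baseline correlations (0.7 to 0). This is a cheap improvement to the analysis text. It is not a defect in safety monitoring or in the primary analysis.

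**What to change.** In section 13.2, and in the SAP to match:

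- For thyroid function, glucose and insulin, limit the cross-reference to the baseline-adjusted ANCOVA model and exempt these variables from the Hochberg step.
- Report each dose-versus-placebo difference at three and six months with an unadjusted 95% confidence interval, labelled as not adjusted for multiplicity.
- Base the group-level safety statement on those intervals, not on the absence of significance.
- Keep Hochberg for the efficacy endpoints.

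This takes a sentence or two and needs no new data. The cost is the higher false-alarm rate per variable and visit shown above, which accumulates over variables and visits; the labelling is there so that an isolated nominal finding is read in that light.

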20. WITHDRAWAL

Participants will be withdrawn at the participant's request, if they have a serious adverse reaction, if they develop diabetes or thyroid dysfunction, if they lose capacity, if they require treatment with medication on the prohibited list or if they develop any new medical problems which would render the study measurements invalid.

If IMP is stopped, and if the participant is willing, wherever possible they will be asked to continue to complete study assessments unless the PI judges this to be inappropriate due to the participant's health or personal circumstances. This decision will be documented in the CRF and site file, reported to the DMEC and included in the final study report.

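### The protocol is inconsistent on whether women who develop diabetes or thyroid dysfunction stop only study drug or also leave follow-up; applying Hochberg to the safety measures is a lesser point (minor)

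*Protocol*

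**What the plan says.** **Role of the measures.** Thyroid and diabetes safety is a named objective in Section 5. Section 12 makes it a formal comparison: "We will analyse between-group differences in change in thyroid function tests and blood glucose as a secondary endpoint". Section 13.2 sets the method: "thyroid function, glucose and insulin at three and six months: analysis as described for the primary endpoint". That method is baseline-adjusted ANCOVA, and it includes this sentence: "The Hochberg procedure will be used to account for multiple comparisons".

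**What happens to a woman who develops one of these harms.** Four statements apply:

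- Section 11.7 covers harms found on safety bloods, "or a new diagnosis reported by participant at monthly contact), their treatment will be stopped".
- Section 12: "We will withdraw participants who develop thyroid dysfunction or diabetes during the study".
- Section 20, first paragraph, gives the reasons for withdrawal, among them "if they have a serious adverse reaction, if they develop diabetes or thyroid dysfunction, if they lose capacity".
- Section 20, second paragraph, says of willing women whose study drug is stopped that "wherever possible they will be asked to continue to complete study assessments unless the PI judges this to be inappropriate".

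**Timing.** After baseline, Appendix 2 schedules glucose, insulin, HbA1c and TSH only at 13 and 26 weeks.

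**The concern.** One event leads to two different instructions. Staff who follow Section 12 could end a woman's participation. Staff who follow Section 11.7 and the second paragraph of Section 20 would stop her capsules and still ask her back at 26 weeks.

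Under the first course her 26-week value is missing because of the outcome being measured. Women who were harmed drop out of the six-month safety comparison and women who were not harmed stay in, so any bias runs towards no harm. Her six-month NTX value is lost as well, although Section 13.2 plans an intention-to-treat analysis of all randomised participants. An analysis plan can choose how to handle missing values, but it cannot restore values that were never collected. The matter therefore belongs in the protocol.

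The lesser issue is Hochberg. It limits false positive claims. Carried over to a safety measure, it makes a harm confined to one dose harder to flag.

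**Working it through.** **1. The texts side by side**

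| Place | Consequence of new diabetes or thyroid dysfunction |
|---|---|
| 11.7 | Study drug stops |
| 12 | Participant withdrawn |
| 20, first paragraph | Participant withdrawn, in the same list as loss of capacity |
| 20, second paragraph | If study drug is stopped, assessments continue where possible |

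The protocol does not define withdrawal. Where it gives the scope, it means leaving: Section 11.10 (missed safety monitoring) refers to the trial and Section 16.3 (loss of capacity) to the study. Sections 12 and 20 give no scope for these two harms.

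A woman whose harm is found at the 13-week visit has one scheduled thyroid and glucose measurement left, at 26 weeks. Her 13-week value is already in hand and stays in the three-month comparison.

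**2. Size of the withdrawal effect**

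The protocol gives no SD, harm size or power for thyroid or glucose measures, so there is no stated figure to reproduce. The effects below are assumptions, in units of the residual SD.

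Inputs: 120 women randomised equally to three arms (Sections 13.1 and 17), so 120 / 3 = 40 per arm. In one active arm, k women are shifted by 3 SD at 13 weeks. A fraction f of that shift remains at 26 weeks. Tests against placebo use the pooled variance at two-sided 5%, unadjusted, by simulation.

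Mean difference at six months if the women are kept = k × 3 × f / 40. For k = 4 and f = 1 this is 4 × 3 / 40 = 0.30 SD. If all k are dropped it is 0.

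| k of 40 | Kept, f = 1 | Kept, f = 0.5 | Kept, f = 0 | All dropped |
|---|---|---|---|---|
| 2 | 8% | 6% | 5% | 5% |
| 4 | 19% | 9% | 5% | 5% |
| 6 | 38% | 15% | 5% | 5% |

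Entries are the chance of flagging the harm. Section 11.7 stops the drug on either reading, so a retained woman's 26-week value is taken about 26 − 13 = 13 weeks off drug. Persistence is therefore the key unknown.

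**3. Cost of Hochberg on the safety measures**

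There are two dose-placebo comparisons. If only one dose does harm, the other p-value is usually above 0.05, so the harmful dose must reach 0.025.

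Approximate power = Φ(δ√(n/2) − z), with n = 40, so √(n/2) = √20 = 4.472, and z = 1.960 (5%) or 2.241 (2.5%). For δ = 0.634: 0.634 × 4.472 = 2.835. Then Φ(0.875) = 81% and Φ(0.594) = 72%. Simulation with a shared placebo arm and pooled variance gives:

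| Harm | Unadjusted | Hochberg |
|---|---|---|
| One dose, 0.5 SD | 60% | 49% |
| One dose, 0.634 SD | 80% | 72% |
| One dose, 0.8 SD | 94% | 91% |
| Both doses, 0.634 SD (per dose) | 80% | 78% |
| None: at least one false signal per measure | 9.1% | 4.8% |

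**The case against.** **The texts can be reconciled.** Section 11.7 is the operative rule for these two events and says only that treatment stops. The second paragraph of Section 20 then makes retention the default for willing women. An exception needs a documented decision by the principal investigator, reported to the DMEC. A reader might infer that the protocol ends follow-up for women who are harmed, but no sentence says so. This stands. What remains is ambiguity, sharpened because Section 20 lists these harms beside loss of capacity, which Section 16.3 treats as leaving the study.

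**The fall from 19% to 5% is the unfavourable end.** A reader might take it as the size of the bias. It needs all four women to leave at 13 weeks and the whole shift to last about 13 weeks off drug. With half the shift remaining the comparison is 9% against 5%, and with full reversal there is no difference. Even 19% shows that this test would usually miss such a harm with complete follow-up. This also stands.

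**Other safeguards exist.** Doctors assess out-of-range values (Section 10.2), adverse events are recorded (Section 19.1), and the DMEC sees unblinded glucose, insulin and thyroid data (Section 23). Individual cases would not be hidden.

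**Hochberg is a trade-off.** It changes a significance label and leaves the estimates intact. Removing it buys sensitivity at the price of more false signals, across several measures and two visits.

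**Two further inferences are not supported.** One is that the protocol is at fault for comparing means, which can cancel TSH shifts in opposite directions, without tabulating out-of-range counts. Such tables are ordinary analysis-plan content, and nothing in the protocol rules them out. The other is that the safety analysis is confined to women with selenium below 120 mcg/l. Section 6 ties that restriction to the primary endpoint efficacy analysis.

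**Conclusion.** The inconsistency is real and should be corrected, but it is minor. Taken literally, Sections 12 and 20 could lose the 26-week thyroid, glucose and NTX values of women in whom harm appeared, and so bias the six-month safety comparison towards no harm. With 4 of 40 women affected at an assumed 3 SD, the loss in the chance of flagging the harm runs from nothing (full reversal off drug) to about 14 percentage points (full persistence, 19% − 5%). For women withdrawn at the 13-week visit, the three-month comparison is unaffected, and so are adverse event recording and DMEC review.

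The use of Hochberg on the safety measures is explicit in Section 13.2 but secondary. It costs about 3 to 11 points of power for a harm at one dose of 0.5 to 0.8 SD, and about 2 points if both doses harm equally at 0.634 SD. All effect sizes are assumptions, because the protocol gives none.

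**What to change.** **Main change.** Reword Sections 12 and 20 to agree with Section 11.7. New diabetes or thyroid dysfunction stops study drug but does not end follow-up, and the 26-week assessments are still sought from willing women. The existing exception for health or personal circumstances can stay. The cost is two wording changes, since the 26-week visit is already scheduled.

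**Secondary change.** In Section 13.2, report the thyroid, glucose and insulin comparisons with unadjusted p-values and confidence intervals. Keep the ANCOVA, and keep Hochberg for the primary endpoint. The cost is a rise in the chance of at least one false safety signal from about 5% to 9% per measure, so an isolated signal should be read with that in mind.
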